2.3. Clinical Study Protocol (CSP) and CSP Amendments

This SAP was based on the protocol version 2.0 / Amendment 1, dated 17-mar-2023.

2.4. Schedule of Assessments

2.4.1. Regular Schedule of Activities

EVENT	SCREENING PERIOD		TREATMENT PERIOD						FOLLOW-UP PERIOD	
	S1 ^a	S2	Day 1 ^b	W4	W12 and then every 12 weeks	W24 and then every 24 weeks	W48 ^c and then every 48 weeks	ED	EoT ^d	4 weeks after last IP dose (EoS)
Study Day (D)/ Week (W)										4 weeks after last IP dose (EoS)
	S1 ^a	S2	Day 1 ^b	W4	W12 and then every 12 weeks	W24 and then every 24 weeks	W48 ^c and then every 48 weeks	ED	EoT ^d	
	D-28 to D-1			± 3 days	± 7 days	± 7 days	± 7 days			± 3 days
Informed consent	✓									
TB assessment ^e	✓ ^f						✓		✓	
Sigmoidoscopy ^g including biopsy collection	✓ ^h						✓	✓ ⁱ		

^a Screening visit 1 (S1) may occur at the same time as any scheduled visit of the SELECTION-LTE study or as a separate visit.

^b Screening visit 2 (S2) and the Day 1 visit can occur on the same day or on 2 consecutive days.

^c After unblinding at the study primary analysis time point, subjects will receive unblinded treatment and the frequency of study visits will be reduced to every 24 weeks with an allowed window of ±10 days (see CSP Section 8.1.4).

^d In countries where filgotinib becomes commercially available, the study will be terminated for the subjects who have already completed at least 48 weeks of treatment.

Subjects will then be requested to attend the EoT visit as soon as possible (see CSP Section 5.1). For the subjects who have not yet completed 48 weeks of treatment when filgotinib becomes commercially available, the Week 48 visit can replace or occur on the same day as the EoT visit. All assessments listed at the EoT visit can be conducted as part of the Week 48 visit; therefore EoT assessments do not need to be repeated.

^e Subjects who have been previously treated for TB with a complete and adequate course of therapy as per local standard of care and as verified by the investigator and do not need to have yearly QuantiFERON® tests should only be screened for signs and symptoms of reactivation at the time of screening and at visits as indicated in the Schedule of Activities.

^f Blood sample for QuantiFERON® test, if applicable, at S1 needs to be taken after signing ICF, preferably 4 weeks before Day 1 to obtain the TB assessment result before randomization. An indeterminate result should be repeated once and the second result (if positive or negative) will be accepted. Subjects who had 2 sequential indeterminate QuantiFERON® tests or a positive QuantiFERON® test during any of the visits of the SELECTION-LTE but do not have active or latent TB at the time of screening, as verified by the investigator, or had latent TB and underwent adequate treatment and continued in the SELECTION-LTE, are not required to have a screening QuantiFERON® test. In this case, the subject must be screened for signs and symptoms of TB reactivation.

EVENT	SCREENING PERIOD		TREATMENT PERIOD						FOLLOW-UP PERIOD	
	S1 ^a	S2	Day 1 ^b	W4	W12 and then every 12 weeks	W24 and then every 24 weeks	W48 ^c and then every 48 weeks	ED	EoT ^d	4 weeks after last IP dose (EoS)
Study Day (D)/ Week (W)										
			Day 1 ^b	W4	W12 and then every 12 weeks	W24 and then every 24 weeks	W48 ^c and then every 48 weeks	ED	EoT ^d	4 weeks after last IP dose (EoS)
	D-28 to D-1			± 3 days	± 7 days	± 7 days	± 7 days			± 3 days
Inclusion/exclusion criteria	✓		Prerandomization							
Demographics	✓									
Medical history	✓									
Pregnancy test	✓ ^j			✓ ^j	✓ ^j			✓ ^j	✓ ^j	✓ ^j
FSH test ^k	✓									
Physical examination (symptom-directed)		✓ ^l		✓	✓			✓	✓	✓
Vital signs		✓ ^l		✓	✓			✓	✓	✓
Height	✓									
Weight	✓ ^l			✓	✓			✓	✓	✓
Hematology		✓ ^{l, m}		✓	✓			✓	✓	✓

^g Sigmoidoscopy during screening, at Week 48 and every 48 weeks thereafter, and ED (if applicable), in fasting condition, as per local guidance. In case of a suspected UC flare, an additional sigmoidoscopy is needed. Two biopsies should be collected during every sigmoidoscopy performed during the study.

^h Bowel preparation for screening sigmoidoscopy can only start after signing ICF.

ⁱ Subjects who discontinue the study prior to Week 48 require a sigmoidoscopy at the ED visit.

^j WOCBP only. Serum pregnancy test during screening; urine dipstick pregnancy test at the Week 4 visit, thereafter at the site every 12 weeks, and in-between every 4 weeks at home (±3 days). If a urine test cannot be confirmed as negative (e.g. an ambiguous result), a serum pregnancy test is required to confirm.

^k For postmenopausal women only.

^l Could be taken from SELECTION-LTE. In case assessments listed at S2 are conducted as part of the EoT visit in SELECTION-LTE, the assessments do not need to be repeated and assessment results may be used.

^m Screening clinical laboratory results may only be available after randomization. In that case, these results will be reviewed after randomization and subjects with laboratory results meeting discontinuation criteria, will be discontinued from the study.

EVENT	SCREENING PERIOD		TREATMENT PERIOD						FOLLOW-UP PERIOD	
	S1 ^a	S2	Day 1 ^b	W4	W12 and then every 12 weeks	W24 and then every 24 weeks	W48 ^c and then every 48 weeks	ED	EoT ^d	4 weeks after last IP dose (EoS)
	D-28 to D-1			± 3 days	± 7 days	± 7 days	± 7 days			± 3 days
Chemistry		✓ ^{l, m}		✓	✓			✓	✓	✓
Lipid profile (fasted ⁿ)		✓ ^{l, m}				✓			✓	
Urine analysis		✓ ^{l, m}				✓			✓	
HBV DNA monitoring ^o		✓ ^l			✓				✓	
12-lead ECG		✓ ^l					✓		✓	
Serum immunoglobulin		✓ ^l				✓			✓	
CRP		✓ ^l		✓	✓			✓	✓	
Fecal calprotectin ^p	✓ ^q	✓ ^{l, r}		✓	✓			✓	✓	

ⁿ Subjects should remain fasted for at least 8 hours, excluding water.

^o Only subjects with positive HBcAb and HBV DNA <LLOQ in a parent UC study will require ongoing HBV DNA monitoring every 12 weeks during the present study, and after study primary endpoint unblinding every 24 weeks.

^p Stool samples need to be taken prior to bowel preparation for endoscopy. Stool samples can be collected within 24 hours prior to the visit or during the visit.

^q FCP should be assessed during screening if the last assessment during SELECTION-LTE was >6 months prior to screening or the most recent value was >250 µg/g.

^r This FCP assessment should be obtained at the EoT visit in SELECTION-LTE (i.e. performed after the subject is fully eligible to roll over to the present study) and will be the baseline of the present study. In case FCP was not obtained at the EoT visit of SELECTION-LTE, an unscheduled stool sample should be collected within 24 hours prior to or during Day 1 (i.e. predose).

EVENT	SCREENING PERIOD		TREATMENT PERIOD						FOLLOW-UP PERIOD	
	S1 ^a	S2	Day 1 ^b	W4	W12 and then every 12 weeks	W24 and then every 24 weeks	W48 ^c and then every 48 weeks	ED	EoT ^d	4 weeks after last IP dose (EoS)
Study Day (D)/ Week (W)					± 3 days	± 7 days	± 7 days			± 3 days
	S1 ^a D-28 to D-1	S2	Day 1 ^b	W4	W12 and then every 12 weeks	W24 and then every 24 weeks	W48 ^c and then every 48 weeks	ED	EoT ^d	4 weeks after last IP dose (EoS)
e-Diary instruction & review ^u			✓	✓	✓			✓	✓	✓
modified Mayo Clinical Score ^w		✓					✓	✓		
Randomization ^y			✓							
Dispense IP			✓	✓	✓ ^z					
Review IP compliance				✓	✓			✓	✓	

^u Training and dispensation of the e-Diary on Day 1; review subject e-Diary and retrain, if necessary, at all subsequent time points; return of e-Diary at EoS (follow-up visit). Subjects will record the following in the e-Diary: stool frequency, rectal bleeding, and normal stool count.

^w mMCS calculation during screening (baseline value for all subjects), every 48 weeks, and at ED visit (if applicable). Screening mMCS will be calculated using rectal bleeding, stool frequency subscores from SELECTION-LTE during the screening period, and endoscopic subscore from screening sigmoidoscopy. mMCS at other study specified timepoints will be calculated using rectal bleeding, stool frequency, and endoscopic subscores during the present study.

^y Randomization only after performing all screening procedures and after completion of the EoT visit in SELECTION-LTE.

^z Frequency of IP dispensation after study unblinding at the primary analysis time point will be every 24 weeks.

EVENT	SCREENING PERIOD		TREATMENT PERIOD						FOLLOW-UP PERIOD	
	S1 ^a	S2	Day 1 ^b	W4	W12 and then every 12 weeks	W24 and then every 24 weeks	W48 ^c and then every 48 weeks	ED	EoT ^d	4 weeks after last IP dose (EoS)
Study Day (D)/ Week (W)				± 3 days	± 7 days	± 7 days	± 7 days			± 3 days
	D-28 to D-1									
Concomitant medications	✓ ^v		✓	✓	✓			✓	✓	✓
Dose IP			q.d. throughout the treatment period starting Day 1 ^{aa}						✓	
AE assessment	✓ ^v		throughout the study ^{bb}							

AE: adverse event; CRP: C-reactive protein; ECG: electrocardiogram; ED: early discontinuation; EoS: End of Study; EoT: End of Treatment; FSH: follicle stimulating hormone; HBV: hepatitis B virus; [REDACTED]; IP: investigational product; [REDACTED]; q.d.: once daily; S1: Screening visit 1; S2: Screening visit 2; TB: tuberculosis; UC: ulcerative colitis.

^{aa} If on Day 1 the subject has already taken the IP as assigned in the SELECTION-LTE study, the first dose as assigned in this study should be taken on Day 2.

^{bb} AEs ongoing at the end of the subject's participation in the SELECTION-LTE study should be recorded as medical history.

2.4.2. Schedule of Activities After Re-escalation

Event	TREATMENT PERIOD					After Week 12: Continue with the regular Schedule of Activities, starting with assessments of the next 12-weekly visit until end of the study
	baseline	W2 ^a	W4	W8	W12	
Study Day (D)/ Week (W)		± 3 days	± 3 days	± 7 days	± 7 days	
Physical examination (symptom-directed)	✓		✓	✓	✓	
Vital signs	✓		✓	✓	✓	
Weight	✓		✓	✓	✓	
Hematology	✓		✓	✓	✓	
Chemistry	✓		✓	✓	✓	
Urine pregnancy test ^b	✓		✓	✓	✓	
CRP	✓		✓	✓	✓	
e-Diary instruction & review	✓	✓	✓	✓	✓	

^a Phone contact

^b Only for women of childbearing potential

Event	TREATMENT PERIOD				
	baseline	W2 ^a	W4	W8	W12
Study Day (D)/ Week (W)		± 3 days	± 3 days	± 7 days	± 7 days
Dispense IP	✓		✓	✓	✓
Concomitant medications	✓	✓	✓	✓	✓
Dose IP	q.d. starting from dispensing of unblinded re-escalated IP ^c				
AE assessments	throughout the study				

AE: adverse event; CRP: C-reactive protein; [REDACTED]; q.d.: once daily.

^c If the subject has already taken IP on the re-escalation baseline day, the first adjusted dose should be taken on Day 2 of re-escalation.

2.4.3. Sample Size Justification

The sample size is determined based on the desired level of precision (half width of the 95% CI) of the estimated treatment difference between 200 mg filgotinib q.d. and 100 mg filgotinib q.d. in the percentage of subjects meeting corticosteroid-free^a mMCS remission criteria at Week 48. The level of precision determines the range in which the treatment difference is estimated to be. This range is expressed in percentage points.

The highest variability in the estimation of the treatment effect (i.e. CI with the lowest precision, or largest width) is observed when the remission rate is 50%. A sample size of 40 subjects per group will guarantee a worst-case precision of maximum 22.5% (CSP section 9.1).

Due to early termination of the study, the sample size was limited to 22 randomized subjects.

2.5. Randomization and Blinding

When a subject is confirmed to be eligible for the clinical study (CSP section 6.1 and 6.2), the subject will be randomized. Subjects will be randomized in a 1:1 ratio to 200 mg or 100 mg filgotinib q.d. Subjects will be stratified according to ES (score of 0 or 1) at baseline to ensure treatment balance in each stratum.

The subjects and the entire clinical study team, including the investigators, clinical study coordinators, and sponsor personnel are blinded to treatment assignment until the study primary analysis time point, with the exception of the sponsor's clinical study supply leader.

Due to early termination of the study however, the unblinding is to take place prior to the study primary analysis time point. Further details on blinding are described in section 6.4.2 of the CSP.

3. STUDY ESTIMANDS

For an overview of the planned estimands to be analyzed, see CSP section 9.3.4. Due to the early termination of the study however, a different analysis approach will be taken which will be detailed in section 6.

4. GENERAL METHODOLOGY

4.1. Analysis Sets

The analysis set will always be indicated in a subtitle in the table, listing or figure.

4.1.1. All Screened Analysis Set

All subjects who signed an informed consent form to participate in this study.

^a Free of corticosteroids for at least 12 weeks.

4.1.2. All Randomized Analysis Set

All screened subjects who were randomized in this study.

4.1.3. Safety Analysis Set

All randomized subjects who were administered study drug at least once (Same as Full Analysis Set).

4.1.4. Full Analysis Set

All randomized subjects who were administered study drug at least once.

[REDACTED]

[REDACTED]

[REDACTED]

4.2. Randomized Versus Actual Treatment Group

For subject information, efficacy and safety parameters, the treatment group as assigned by the randomization will be used in the analysis (i.e. as-randomized analysis).

Differences between the randomized and actual assigned treatment group (disregarding any difference between randomized treatment and actual treatment due to dose re-escalation) will be listed.

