The primary efficacy estimand for the primary endpoint targets to estimate the effect of decreasing the filgotinib dose from 200 mg q.d. to 100 mg q.d. versus remaining on 200 mg q.d. on corticosteroid-free mMCS remission without ES-confirmed flare or discontinuation of treatment at Week 48, regardless of treatment interruptions, in subjects who are in stable clinical remission at study entry. The effect size will be estimated using the Mantel-Hanszel method and expressed as a difference in proportions.

The secondary estimand for the primary endpoint targets to estimate the effect of decreasing the filgotinib dose from 200 mg q.d. to 100 mg q.d. versus remaining on 200 mg q.d. on corticosteroid-free mMCS remission at Week 48, regardless of flare, permanent treatment discontinuation, or temporary treatment interruptions, in subjects who are in stable clinical remission at study entry. The effect size will be estimated using the Mantel-Hanszel method and expressed as a difference in proportions.

Secondary endpoints

Estimands for the secondary efficacy endpoints are described in the protocol.

Safety analysis

Safety data will be summarized descriptively by treatment group according to the filgotinib dosing regimen actually received at randomization.

For the primary safety analysis, any data collected after ES-confirmed UC flare will not be included in the analyses.

For the secondary safety analysis, data will be included regardless of flare.

Additionally, safety data may be analyzed in the subgroup of subjects who are initially assigned to 100 mg filgotinib q.d. and are re-escalated later to 200 mg q.d. in the safety analysis set.

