9. STATISTICAL METHODS

All statistical methods shall be detailed in a statistical analysis plan (SAP). The SAP will be finalized prior to the interim analysis (see Section 9.3.2) and unblinding. All relevant data collected in this clinical study will be documented using summary tables, figures, and subject data listings.

Any deviations from the CSP are to be justified in the SAP.

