9.3.5. Analyses of Safety Data

All safety analyses will be performed using the safety analysis set (Section 9.2.4). All safety data will be summarized descriptively by treatment group according to the filgotinib dosing regimen actually received at randomization.

For the primary safety analysis, any data collected after ES-confirmed UC flare will not be included in the analyses.

For the secondary safety analysis, data will be included regardless of flare.

Additionally, safety data may be analyzed in the subgroup of subjects who are initially assigned to 100 mg filgotinib q.d. and are re-escalated later to 200 mg q.d. in the safety analysis set.

Missing data for safety endpoints will not be imputed.

Clinical safety will be addressed by assessing AEs, laboratory assessments, physical examinations, ECG, and vital signs.

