4.5. Presentation of Results

4.5.1. Presentation of Treatment Groups

In the section Subject Information (excluding Concomitant Medications), a grand total “All Subjects” will be added to summarize all subjects over all treatment groups in tables and figures.

Treatment groups will be presented as randomized, regardless of potential treatment switches to open-label 200 mg filgotinib.

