6.4	Frequency and severity of treatment-emergent adverse events (TEAEs), treatment-emergent SAEs, and TEAEs leading to treatment discontinuation.	Safety data will be summarized descriptively by treatment group according to the filgotinib dosing regimen actually received at randomization. For the primary safety analysis, any data collected after ES-confirmed UC flare will not be included in the analyses. For the secondary safety analysis, data will be included regardless of flare.	Only the primary safety analysis will be conducted. Vital signs and ECG data will be listed

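### SAP 4.2 and 4.5.1 tabulate safety by randomised arm where protocol 9.3.5 uses the regimen actually received, and the change is neither declared nor justified

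*SAP*

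**What the plan says.** **Protocol.** Section 9.3.5 sets the rule for safety: "All safety data will be summarized descriptively by treatment group according to the filgotinib dosing regimen actually received at randomization". The synopsis says the same. Section 9 adds a condition on the SAP: "Any deviations from the CSP are to be justified in the SAP".

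**SAP, operative rule.** Section 4.2 reads: "For subject information, efficacy and safety parameters, the treatment group as assigned by the randomization will be used in the analysis". Section 4.5.1 agrees: "Treatment groups will be presented as randomized, regardless of potential treatment switches to open-label 200 mg filgotinib". Section 4.2 also anticipates mismatches other than re-escalation. It describes them as "Differences between the randomized and actual assigned treatment group" and sends them to a listing.

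**SAP, declared changes.** Section 6.1 presents Table 5 as the summary of modified analyses. In the safety row, the planned-analysis column repeats the protocol's received-regimen wording. The revised column says "Only the primary safety analysis will be conducted" and moves vital signs and ECG to listings. It does not mention grouping.

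**SAP, analysis set.** Section 4.1.3 defines who enters the safety set (randomised and dosed at least once). It does not say under which arm a subject is counted.

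**The concern.** Grouping by assigned arm and grouping by regimen received are different rules, and they part company exactly when a subject gets the wrong blinded kits. The protocol chose the second for safety and the SAP applies the first. Someone checking Table 5 to see what changed would conclude that the safety grouping was untouched.

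Most of what the SAP still tabulates by arm is safety. The primary endpoint, IBDQ and both flare endpoints are reduced to listings, and among efficacy endpoints only CRP and FCP are summarised by group. The rule therefore governs the TEAE tables (SAP 6.4.1.8), the adverse events of interest (6.4.1.7) and the laboratory summaries and grades (6.4.2.9). The exposure tables in 6.2.6 raise the same question. If a wrong-regimen subject existed, these tables would attribute that subject's events to a dose not taken.

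**Working it through.** **1. Comparing the rules**

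| Place | Grouping for safety |
|---|---|
| Protocol synopsis and 9.3.5 | Regimen actually received at randomization |
| SAP Table 5, planned column | Same, restated from the protocol |
| SAP Table 5, revised column | Silent; primary safety analysis kept |
| SAP 4.2 and 4.5.1 | As randomised |

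The conflict is between protocol and SAP. For Table 5 the fault is an omission.

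**2. Is a justification given elsewhere in the SAP?** Section 3 announces a different approach because of early termination, but it refers to the estimands of CSP 9.3.4, which are efficacy estimands. Section 6.1 gives early termination as the reason for limiting and modifying analyses. That explains listings in place of models. It does not explain counting safety by a different arm.

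**3. Is re-escalation the reason?** The protocol rule is tied to the regimen at randomization, so it already ignores the later switch to open-label 200 mg. SAP 6.4.1.8 focuses the AE tables on the period up to ES-confirmed flare. SAP 4.2 excludes re-escalation from its mismatch listing. What remains is a wrong initial regimen.

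**4. Size if one such subject exists**

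The documents give no figure to reproduce on this point, so this is an illustration.

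*Inputs.* 22 randomised (SAP 2.4.3) and 1:1 allocation (SAP 2.5). The actual split is not given; 11 per arm is assumed, so one subject is 1/11 = 9.1% of an arm. Also assumed: one subject randomised to 200 mg received 100 mg and had the event, with a other subjects with the event in the 200 mg arm and b in the 100 mg arm, each from 0 to 6.

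*Difference, 200 mg minus 100 mg:*
- as randomised: (a + 1)/11 − b/11
- by regimen received: a/10 − (b + 1)/12
- shift between the two: 1/11 + 1/12 − a/110 − b/132

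| a, b | As randomised | By regimen received | Shift (points) |
|---|---|---|---|
| 0, 0 | +9.1 | −8.3 | 17.4 |
| 2, 2 | +9.1 (3/11 vs 2/11) | −5.0 (2/10 vs 3/12) | 14.1 |
| 4, 4 | +9.1 | −1.7 | 10.8 |
| 6, 6 | +9.1 | +1.7 | 7.4 |

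The shift is linear in a and b, so 7.4 and 17.4 are the extremes over this range.

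*Direction.* If the subject was randomised to 100 mg and received 200 mg, the same algebra gives the opposite sign. With a = b = 2, the difference is 2/11 − 3/11 = −9.1 as randomised and 3/12 − 2/10 = +5.0 by regimen received, a shift of −14.1 points.

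**5. Size if no such subject exists.** The two groupings coincide and every table is identical.

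**The case against.** The best defence starts from the protocol's wording. Elsewhere the documents speak of the treatment at randomization to separate the initial arm from open-label 200 mg after a flare, and the sentences that follow in 9.3.5 concern flare and re-escalation. On that reading the rule only means the initial arm ignoring re-escalation, and the SAP agrees with it. The phrase is loosely worded, but this reading leaves the words about actual receipt with no work to do. SAP 4.2 itself treats randomised and actual assigned treatment as different things.

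The second defence is that the effect is hypothetical and partly covered. Allocation runs through a central system and the documents report no mis-dispensing. Mismatches, major protocol deviations, randomisation codes and serious events are all listed. With 22 subjects a careful reader could find an affected subject. All of this stands, and it limits the expected numerical effect. A listing makes the mismatch visible but leaves the tables uncorrected.

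Three stronger readings are tempting and should not be drawn:
- **That Table 5 itself orders grouping by dose received.** It restates the protocol rule in the planned column and is silent in the revised one, while 4.2 and 4.5.1 are explicit and agree with each other.
- **That as-randomised grouping pulls the arms together.** That is the expected tendency when risk differs by dose, but it need not hold for one subject. In the a = b = 2 example the as-randomised gap (9.1 points) is larger than the gap by regimen received (5.0 points).
- **That subjects were in fact given the wrong dose.** Nothing in the documents says so.

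**Conclusion.** The point holds as an undeclared and unjustified departure of the SAP from the protocol on how safety is grouped. It is worth correcting because safety makes up most of the remaining by-arm tabulation and the correction is cheap.

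Its numerical effect depends on a mismatch that the documents do not report. With none, nothing changes. With one wrong-regimen subject who has the event, the between-arm difference moves by roughly 7 to 17 percentage points, in a direction set by which arm the subject was randomised to. That range assumes 11 per arm and 0 to 6 other cases in each arm. Safety is descriptive with no formal testing, so no test result is at risk. What is at risk is attribution of events to dose.

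**What to change.** In SAP 4.2 and 4.5.1:
- keep as-randomised grouping for efficacy and subject information;
- tabulate safety (AEs, adverse events of interest, laboratory) by the initial blinded filgotinib regimen actually received, disregarding re-escalation, in line with CSP 9.3.5;
- state that the exposure tables in SAP 6.2.6 follow the safety grouping, because the SAP files them under subject information and the rule would otherwise be ambiguous;
- state that isolated kit errors after the first dispensing do not change a subject's group and are listed, since IP is dispensed repeatedly from Day 1 onward;
- keep the listing of randomised versus actual assignment.

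If the sponsor prefers as-randomised grouping for safety, the minimum is to declare it in the safety row of Table 5 with a reason. That meets the protocol's justification requirement, but it leaves any wrong-regimen subject's events under the assigned dose.

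The cost is a few sentences and one treatment variable, which the discrepancy listing already needs. The small downside is that the safety groups may differ from the randomised groups by any mis-dispensed subject, so denominators could differ between efficacy and safety tables and would need a footnote.
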